13 SAFETY MONITORING AND REPORTING

13.1 Dose-limiting Toxicity

DLTs will be evaluated according to NCI CTCAE (Version 5.0) criteria.

A DLT will be defined as a possibly, probably or definitely drug-related:

- Grade IV toxicity (with the exception of grade IV cerebral edema) or any non-neurologic toxicity \geq Grade III toxicity of any duration.
- Grade III neurologic toxicity if not improved to Grade \leq II within 7 days of clinical management will be declared a DLT.

Neurotoxicity that improves to Grade II within 7 days will be allowed an additional 21-day management period to resolve to a Grade I or return to patient baseline. If the event does not improve to a Grade I or return to patient's baseline within 21 days of management, it will then be declared a DLT

Immune-related neuro toxicities are a recognized adverse event associated with immunotherapy. Symptoms may present throughout the course of treatment and involve the peripheral and central nervous system, and usually respond well to steroids, if started early. Early recognition of neurological toxicity is critical for the initiation of clinical management or surgical intervention to prevent or potentially reverse neurological sequelae. If neurological toxicity improved to \leq Grade I within 28 days of clinical management, patient may resume treatment.

Non-neurologic Grade III and any Grade IV toxicity or any life-threatening event not attributable to a concomitant medication, co-morbid event, or disease progression, even if reversible, will be considered a DLT. If biopsy cannot be obtained, any new radiographic or clinical changes not attributable to tumor progression that produce a non-neurologic Grade III or any Grade IV or life-threatening toxicity will be considered a DLT. Life-threatening events, as described above, even if considered a Grade III toxicity, will still be considered a DLT even if reversible and in such cases no further vaccinations will be given.

If a **neurologic Grade III NCI CTC toxicity** is seen that is not attributable to a concomitant medication, co-morbid event, or disease progression that has been documented radiographically or clinically, the next immunization for that patient will be withheld for up to 2 months or until the NCI CTC toxicity improves to a Grade \leq I or until the KPS score returns to within 10 points of

baseline. Grade III neurologic toxicities will be declared irreversible if they cannot be reversed within 4 weeks of clinical management. If the event has not improved to a Grade \leq II within 7 days of clinical management (then to \leq Grade I or baseline within 21 days), a DLT will be declared for that patient and no further vaccinations or study-related procedures will be performed. If the event is reversed, but Grade III NCI CTC neurologic toxicity is again seen with subsequent vaccinations, all further vaccinations and study-related procedures will be withheld and a DLT will be declared. Medical therapy or surgical intervention, may be used to reverse any toxicity if necessary.

In the case of hypersensitivity reactions, treatment measures deemed medically appropriate will be initiated and the PI notified of the event. Although not considered a DLT, any patient with \geq Grade II urticaria will not receive further vaccines and will be withdrawn from the study.

Cerebral edema toxicity exception:

Cerebral edema normally presents in glioblastoma patients as part of the disease process and can be exacerbated by standard of care chemotherapy and radiation. Furthermore, an effective anti-tumor immune response may involve inflammatory response and edema in infiltrative tumor cells.

Therefore, we propose that worsening cerebral edema (noted by MRI) that is not associated with changes in neurological symptoms will not constitute a DLT, but worsening cerebral edema in association with Grade 3 or greater other neurologic toxicities will be managed with above outlined criteria (improvement to \leq Grade 2 within 7 days and to Grade 1 or baseline within 21 days or will be declared a DLT). Radiographic improvement of cerebral edema will be noted, but since NCI CTCAE v5.0 guidelines do not allow for an improvement in cerebral edema Grade < 3 , the CTCAE grading criteria for cerebral edema will be exempted from DLT assessment.

Grade III or greater toxicities associated with DC-based immunotherapy have been rare. Adoptive T cell therapy using tumor-infiltrating lymphocytes and high-dose IL-2 in patients with melanoma and treatment with anti-CLTA-4 monoclonal antibody blockade have been the immunotherapy regimens most often associated with treatment related toxicities. To take the most conservative approach to assessing possible toxicities associated with this treatment, we will be vigilant for any similar toxicity associated with this therapy, in addition to autoimmune toxicity specific to the CNS. Possible immune-mediated disorders that have been observed in patients who have received immunotherapy in early phase trials have involved the skin (vitiligo and cutaneous leukocytoclastic vasculitis), the thyroid gland (autoimmune thyroiditis), the liver (autoimmune hepatitis) and the pituitary (hypophysitis). Abnormal lab results, which may be immune-mediated, include elevations of serum lipase and amylase and liver function tests. If a patient has an AE that is thought to be possibly related to autoimmune antibodies (eg, thyroiditis, hepatitis, thrombocytopenia) the PI will send a blood sample for appropriate autoimmune antibody testing. If specific autoantibodies are present, the serum sample taken for storage at baseline will be tested for the presence of those autoantibodies. Further immunotherapy treatment in that patient will be held until the etiology of the event is established.

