8 SUBJECT ELIGIBILITY

8.1 Inclusion Criteria

Enrollment and randomization must occur prior to subjects undergoing standard of care chemo-radiation.

All the following inclusion criteria need to be met in order to randomize the subject:

1. Age \geq 18 years.

2. Confirmed diagnosis of de novo Glioblastoma (WHO Grade IV glioma) by histopathology or molecular studies.
(Secondary GBM not eligible).
3. The tumor must have a supratentorial component.
4. Patient must have undergone surgical resection of tumor with less than 3cm x 3cm (9cm²) residual enhancing tumor as product of longest perpendicular planes by MRI.
5. Patients must have recovered from the effects of surgery, postoperative infection, and other complications.
6. A diagnostic contrast-enhanced MRI or CT scan (if MRI is not available) of the brain must be performed preoperatively and postoperatively. Post-op MRI must be performed within 28 days prior to study enrollment. If no post op MRI/CT within 28 days of enrollment is available, a new brain MRI (or CT) must be obtained in order to determine residual burden and eligibility prior to randomization.
Patients unable to undergo MR imaging because of non-compatible devices can be enrolled, provided pre- and post-operative contrast-enhanced CT scans are obtained and are of sufficient quality.
7. Karnofsky Performance Status (KPS) ≥ 70 .
8. Signed informed consent. If the patient's mental status precludes his/her giving informed consent, written informed consent may be given by the legally authorized representative.
9. For females of childbearing potential, negative serum pregnancy test at enrollment (test will be repeated within 72 hours prior to starting TMZ).
10. Women of childbearing potential (WOCBP) must be willing to use acceptable contraceptive method to avoid pregnancy throughout the study and for at least 24 weeks after the last dose of study drug.
Refer to Appendix G for definition of WOCBP and guidance on acceptable contraceptive methods.
11. Males with female partners of childbearing potential must agree to practice adequate contraceptive methods throughout the study and should avoid conceiving children for 24 weeks following the last dose of study drug.
Refer to Appendix G for guidance on acceptable contraceptive methods.

To be assessed prior to initiation of adjuvant TMZ:

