18.5 Appendix E: ECOG Performance Status to Karnofsky Performance Status Comparison Table

Performance Status (PS) will be determined from KPS conversion using the ECOG comparison scale for patients ≤ 50 years

ECOG PERFORMANCE STATUS	KARNOFSKY PERFORMANCE STATUS
0—Fully active, able to carry on all pre-disease performance without restriction	100—Normal, no complaints; no evidence of disease 90—Able to carry on normal activity; minor signs or symptoms of disease
1—Restricted in physically strenuous activity but ambulatory and able to carry out work of a light or sedentary nature, e.g., light house work, office work	80—Normal activity with effort, some signs or symptoms of disease 70—Cares for self but unable to carry on normal activity or to do active work
2—Ambulatory and capable of all selfcare but unable to carry out any work activities; up and about more than 50% of waking hours	60—Requires occasional assistance but is able to care for most of personal needs 50—Requires considerable assistance and frequent medical care
3—Capable of only limited selfcare; confined to bed or chair more than 50% of waking hours	40—Disabled; requires special care and assistance 30—Severely disabled; hospitalization is indicated although death not imminent
4—Completely disabled; cannot carry on any selfcare; totally confined to bed or chair	20—Very ill; hospitalization and active supportive care necessary 10—Moribund
5—Dead	0—Dead

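### Section 13.1 gives conflicting rules for redosing after Grade III neurotoxicity and for Grade IV neurologic events that occur with cerebral edema

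*Combined protocol and SAP*

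**What the plan says.** All of the conflicting text is in the current section 13.1, Dose-limiting Toxicity.

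**Redosing after a Grade III neurologic toxicity**
- The hold on the next immunization has three alternative ends: a 2-month limit, improvement to Grade I or better, or "until the KPS score returns to within 10 points of" baseline.
- An event that has come down to Grade II by day 7 "will be allowed an additional 21-day management period to resolve to a Grade I or return to patient baseline".
- If the toxicity is Grade I or better "within 28 days of clinical management, patient may resume treatment".
- If the 7-day and then the 21-day targets are missed, "a DLT will be declared for that patient and no further vaccinations or study-related procedures will be performed".

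**Grade IV with cerebral edema**
- The DLT definition includes any drug-related "Grade IV toxicity (with the exception of grade IV cerebral edema" itself).
- A later paragraph repeats the rule, starting "Non-neurologic Grade III and any Grade IV toxicity or any life-threatening event not attributable to" other stated causes, and makes such events DLTs even when they reverse.
- The edema exception takes worsening edema accompanied by other neurologic toxicity of Grade 3 and upward, and applies the 7-day and 21-day test. In parentheses it names only that test. The grading exemption at its end covers the edema grade alone.

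**The concern.** The same patient can be handled in two ways, depending on which sentence the site follows.

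On redosing, KPS recovery can end the hold while the neurotoxicity has not resolved by the section's own definition. The next vaccine could be given, and the same event could then be declared a DLT on day 28.

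On Grade IV with edema, one rule counts a DLT at onset and the other may count none. That affects whether the patient is vaccinated again and whether the event enters the DLT count used in section 13.2.

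Section 9.8 applies the toxicity monitoring and DLT rules to everyone who receives DC vaccine, including patients outside the evaluable set. Section 14.1.1 has one participating site manufacturing under its own IND and doing its own monitoring, so different readings across sites are a practical possibility.

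**Working it through.** **1. Resolution window.** First stage 7 days, second stage an additional 21 days: 7 + 21 = 28 days. This reproduces the 28 days in the resumption sentence.

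**2. The two redosing rules applied to one patient.** Suppose Grade III neurotoxicity begins just after vaccine #1, is Grade II on day 7 (above the patient's baseline), and KPS is within 10 points of baseline on day 14, when vaccine #2 is due.

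| Rule in 13.1 | Status on day 14 |
|---|---|
| Hold sentence, KPS branch | Hold ends; dose can be given |
| Resumption sentence | Not met; not yet Grade I |
| DLT sentence | Still open; DLT on day 28 if not Grade I or baseline |

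The 2-month limit adds nothing, because an event unresolved at 28 days is already a DLT with no further vaccine.

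**3. The KPS branch is not the same as return to baseline.** It accepts a 10-point loss. The entry floor in section 8.1, criterion 7, is 70, and 70 − 10 = 60. Appendix E describes KPS 60 as "Requires occasional assistance but is able to care for most of personal needs" and maps it to ECOG 2. This takes baseline as entry KPS, which section 13.1 does not define.

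**4. When a due dose can meet an open event.** Let D be the interval between doses and o the onset day after the previous dose, with management assumed to start at onset. A due dose falls on management days 7 to 27 when 7 ≤ D − o ≤ 27, that is, D − 27 ≤ o ≤ D − 7 with o ≥ 0. Section 9.8 gives 2 ± 1 weeks for vaccines #2 and #3; section 9.5 gives 35 ± 7 days for later cycles.

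| D (days) | Onset days o |
|---|---|
| 7 | 0 |
| 14 | 0–7 |
| 21 | 0–14 |
| 28 | 1–21 |
| 35 | 8–28 |
| 42 | 15–35 |

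The later cycles are exposed too, because the 28 days run from the start of management and not from the last vaccine. The table shows when the conflict can arise, not how often.

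**5. Grade IV with edema.** Take a related Grade IV non-edema neurologic event with worsening edema that is Grade 2 on day 7 and Grade 1 on day 28. The DLT definition and the paragraph repeating it give a DLT at onset. The edema exception gives no DLT.

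**6. Effect on the stopping boundary.** The smallest printed value in section 13.2 is 3, at N = 3. The version 20201201 amendment entry reports two related events of Grade 3 or above. Even if both were DLTs, 2 < 3.

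The printed boundary was also run exactly for N = 1 to 80. If f(n, k) is the probability of k DLTs after n patients without having stopped, then f(n, k) = (1 − p) f(n − 1, k) + p f(n − 1, k − 1), and any mass with k at or above the boundary for n is counted as stopped.

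| DLT rate p | P(stop) |
|---|---|
| 0.143 (plan: 0.05) | 0.047 |
| 0.271 (plan: above 80% for rates over 27.1%) | 0.800 |
| 0.05 (assumed) | 0.00035 |
| 0.025 (assumed) | 0.000028 |

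The first two rows agree with the plan's own figures. The last two show that stopping is very unlikely at low DLT rates.

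**The case against.** **Redosing.** The KPS sentence may set only how long a dose is withheld, with the resumption sentence the only one that grants permission. On that reading there is no conflict. It does not settle the matter: once a hold ends, the patient returns to the section 9.8 dosing schedule, and the resumption sentence does not say that Grade I is the only route back.

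**Grade IV.** The criteria to which the edema exception refers could be read as including the Grade IV rule, and nothing in the exception expressly lifts that rule. But the parenthesis spells the criteria out as the 7-day and 21-day test alone, and the range upward from Grade 3 takes in Grade IV. This half is closer to loose drafting than the first, but it still leaves open which rule governs.

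**KPS 60.** The floor of 70 is a randomization criterion and is not among the criteria rechecked before adjuvant TMZ. That stands: 60 shows how loose the branch is and does not breach a dosing limit.

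**Existing safeguards.** Section 13.4 requires related events of Grade 2 or above to reach the Coordinating Center within 24 hours, followed by prompt Protocol Chair review. Section 13.1 holds treatment when an event may be related to autoimmune antibodies. These lower the risk, but the first attaches no hold on dosing and the second covers only some events.

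**Size.** The expected number of affected patients is small, and no DLT count after December 2020 is available. Both points stand.

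**Conclusion.** The concern holds. Both conflicts are in the current text of section 13.1, and followed as written a stated rule can redose a patient with unresolved neurotoxicity or drop a Grade IV DLT. The redosing conflict applies to Grade II toxicity above the patient's own baseline; Grade II that equals baseline counts as resolved.

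The practical size is small: few if any patients, on the two related events of Grade 3 or above reported in December 2020, neither stated to be neurologic. Those two could not have reached the section 13.2 boundary. Whether it was approached later cannot be known from the documents. The boundary itself needs no change. This should be corrected because the wording governs patient safety and the correction is nearly free.

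**What to change.** 1. In the hold sentence, release the next vaccine only when the toxicity is Grade I or better, or at the patient's baseline, within 28 days. Delete the stand-alone KPS branch and the 2-month limit. This matches the intent recorded in the version 20190820 amendment entry.
2. In the edema exception, restrict the accompanying neurologic toxicity to Grade 3 and state that Grade IV or life-threatening non-edema neurologic toxicity remains an immediate DLT. Repeat the edema-grade exemption in the paragraph on any Grade IV toxicity, so that the two paragraphs agree. The sponsor should confirm that this is the policy intended, because the same amendment entry records that the DLT criteria were revised in consultation with FDA.
3. Check whether any past neurologic event of Grade 3 or above was released for dosing, or classified, under the conflicting wording.

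The cost is two wording edits and one check of the neurologic events, if there are any. If vaccination has already ended, which the documents do not say, only the check remains.

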13.2 Stopping Rules

To continuously monitor vaccine-related toxicity, we will use a one-sided Pocock-type sequential boundary (Ivanova et al. 2005) to repeatedly test whether a maximum acceptable DLT rate $T=14.3\%$ (1 patient in 7) has been exceeded. The sequential boundary will consist of the minimum cumulative number of patients experiencing DLTs per concurrent number of patients enrolled that would result in a rejection of the null hypothesis $T \leq 14.3\%$ and halting of the trial. The sequential boundary will be adjusted so that the overall probability of stopping the trial across the accrual of all 80 patients in the two treatment arms of the trial (i.e. the overall Type 1 error rate) is 0.05 when $T=14.3\%$. If the trial runs to completion without being halted for excessive toxicity, insight into the magnitude of the true DLT rate can be gained by noting that the sequential boundary established for $T=14.3\%$ has a $>80\%$ overall chance of stopping the trial if in fact T is actually greater than 27.1%. The sequential boundary for $T=14.3\%$ and stopping probability 0.05 is displayed in the following table:

N	1	2	3	4	5	6	7	8	9	10	11	12	13	14	15	16	17	18	19	20
PB	-	-	3	4	4	4	4	5	5	5	6	6	6	6	7	7	7	7	8	8
N	21	22	23	24	25	26	27	28	29	30	31	32	33	34	35	36	37	38	39	40
PB	8	8	9	9	9	9	9	10	10	10	10	11	11	11	11	11	12	12	12	12
N	41	42	43	44	45	46	47	48	49	50	51	52	53	54	55	56	57	58	59	60
PB	12	13	13	13	13	13	14	14	14	14	15	15	15	15	15	16	16	16	16	16
N	61	62	63	64	65	66	67	68	69	70	71	72	73	74	75	76	77	78	79	80
PB	16	17	17	17	17	17	18	18	18	18	18	19	19	19	19	19	20	20	20	20

N = Number of patients enrolled

PB = Pocock boundary, the minimum cumulative number of patients experiencing vaccine-related toxicity that should stop the trial when the concurrent number of patients enrolled in the trial is **N**

The safety monitoring rule described for vaccine-related toxicity was derived using methods described by Ivanova et al. (Ivanova A, BF Qaqish, and MJ Schell, 2005. Continuous toxicity monitoring in phase II trials in oncology. *Biometrics* 61: 540-545). Pocock boundaries were calculated using an online calculator maintained by one of the authors at the UNC Lineberger Comprehensive Cancer Center website:

(<http://cancer.unc.edu/biostatistics/program/ivanova/ContinuosMonitoringForToxicity.aspx>).

